8.1.7 Data listings

All relevant subject data, including those derived, will be presented in individual subject data listings. All listings will be sorted by treatment regimen, investigational site, subject number, date/time and visit. The subject's age will be stated on each listing. Unless otherwise stated, data listings will be based on all subjects randomised.

Unscheduled visit results will be included in date/time chronological order within subject listings, but will not be tabulated.

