If the subject decides to completely withdraw from the study (refuses any further study participation or contact) all study participation for that subject will cease and data to be collected at subsequent visits will be considered missing.

The investigator must also contact the IRT to register the subject's discontinuation from investigational treatment.

If study drug is discontinued prior to the subject's completion of the study, the reason for the discontinuation must be documented in the subject's medical records and entered on the appropriate case report form (CRF) page.

If the subject temporarily discontinues study drug because of AE or SAE or other relevant issue, investigator may restart if considered medically safe and in discussion with the Medical Monitor.

Investigational treatment MAY be permanently discontinued under the following circumstances:

1. Significant worsening of lower extremity oedema (demonstrated by use of the same technique of evaluation for comparison over time and which is not due to local pressure /venostasis effects such as may be caused by socks or other clothing).
2. Significant worsening of obstructive urinary symptoms

Investigational treatment MUST be permanently discontinued under the following circumstances:

3. Total testosterone \geq 1500ng/dL (52 nmol/L) at any two consecutive scheduled visits during the study
4. Liver laboratory values of:
 - ALT or AST >5 times the ULN

If the increase in ALT or AST, is associated with normal bilirubin and ALP, the medical evaluation of withdrawing a patient can be made on a repeat AST/ALT test taken within 48 hours. (Repeated parameters should include: ALT, AST, Alkaline phosphatase and total bilirubin). The subject should interrupt study drug until the repeat liver enzymes are available. If repeat liver parameters are all within the normal range, dosing may be continued. If not normalised the subject should be permanently discontinued.

or

- ALT or AST >3 times the ULN and bilirubin total >2 times ULN or International Normalised Ratio (INR) >1.5 or the appearance of worsening fatigue, nausea, vomiting, right upper quadrant pain/tenderness, fever, rash, or eosinophilia.
 - A hepatic event leading to subject discontinuation should be followed up until event resolution, or becomes not clinically significant
5. Any of the following laboratory abnormalities:
 - Renal function values that require discontinuation:

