7.1.4.5 Potential Hy's Law Criteria

Subjects will be deemed as meeting potential Hy's law Criteria if their ALT or AST > 3x ULN and bilirubin > 2 x ULN at the same visit.

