8.1.3 Descriptive statistics

Continuous variables will be summarised using descriptive statistics including number of non-missing observations (n), arithmetic mean (Mean), median (Median), standard deviation (SD), minimum value (Min), maximum value (Max) and number of missing observations (if any). One additional decimal point for mean and median and 2 additional decimal points for SD will be used.

For categorical variables, summaries will include the number of non-missing observations (n) or the number of patients in the population (N) as applicable, the counts of subjects and percentages. Percentages will be rounded to one decimal place. The number of missing values will be presented as a separate category with no percentage, but only if any missing value is recorded in the data for that summary.

Summary statistics will only be presented at each visit for which the parameter is scheduled to be collected.

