8.1.6 Data re-allocation

The following general rules to handle repeated assessments will be considered:

- 12-lead ECG:
 - in case of multiple measurements associated to the same timepoint (e.g. triplicate ECGs), the average value will be considered for all post baseline HR, RR interval, PR interval, QRS duration, QT interval, QTcB interval and QTcF interval.
- Semen quality analysis/parameters:
 - in case of multiple measurements associated to the same timepoint as permitted by the protocol the average value will be considered for all post baseline semen parameters.

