8.6.3.3 Proportion of subjects that Overshoot Testosterone

The number and proportion of subjects that overshoot testosterone (total testosterone above 1000 ng/dL [35 nmol/L]) at each visit and at least once during the study will be summarised similar to that of the primary endpoint.

In addition the number and proportion of subjects whose maximum testosterone value falls into each of the below categories will be presented by visit and overall during the study:

- ≤ 1500 ng/dl
- $>1500 - <1800$ ng/dL
- $\geq 1800 - \leq 2500$ ng/dL
- >2500 ng/dL

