8.7.2.3 Liver Function

The number and proportion of subjects with laboratory values for liver function and enzymes of clinical concern as follows will be presented descriptively by treatment regimen:

Parameter	Level for clinical concern
ALT	> 1.5 times the upper limit of the normal range (ULN) > 2xULN > 3xULN > 5xULN > 10xULN
AST	> 1.5xULN > 2xULN > 3xULN > 5xULN > 10xULN
Bilirubin Total	> 2xULN > 3xULN
ALT/AST and Bilirubin Total	ALT/AST > 3xULN and Bilirubin Total > 2xULN (assessments to occur at the same visit)

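### The SAP keeps unscheduled results out of every table, so the liver threshold and potential Hy's law counts can miss a limit crossed only on the protocol's 48-hour repeat

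*SAP*

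**What the plan says.** The general rule, in SAP 8.1.7 (Data listings), is: "Unscheduled visit results will be included in date/time chronological order within subject listings, but will not be tabulated". Three other parts of the SAP bear on it.

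- SAP 8.1.3 points the same way: "Summary statistics will only be presented at each visit for which the parameter is scheduled to be collected".
- SAP 8.1.6 opens with "The following general rules to handle repeated assessments will be considered", but then covers only ECGs and semen samples. It has no rule for a repeated laboratory test.
- Appendices E and F set analysis windows for actigraphy and DEXA only.

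The liver table in SAP 8.7.2.3 counts subjects by regimen, not by visit. Its rows are ALT and AST above 1.5, 2, 3, 5 and 10xULN, total bilirubin above 2 and 3xULN, and the combined criterion, which carries the condition "assessments to occur at the same visit". SAP 7.1.4.5 defines potential Hy's law as "ALT or AST > 3x ULN and bilirubin > 2 x ULN at the same visit".

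Protocol 9.3.7 deals with ALT or AST above 5xULN when bilirubin and alkaline phosphatase are normal. In that case "the medical evaluation of withdrawing a patient can be made on a repeat AST/ALT test taken within 48 hours", and "Repeated parameters should include: ALT, AST, Alkaline phosphatase and total bilirubin". Study drug is interrupted until the repeat is available. It may be resumed if all repeat values are normal, and is otherwise permanently discontinued.

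**The concern.** Leaving unscheduled results out of by-visit means is sound practice, because they come from selected men at irregular times. A count of men who ever exceeded a limit asks a different question, and there a filter on visit type can discard the worst value.

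The liver repeat shows why this matters. By definition the triggering sample has normal bilirubin, so it cannot meet the combined criterion. The repeat is the next sample that could meet it, and read literally 8.1.7 keeps that sample out of the table. At stake is a missed case in the rarest and most closely read rows of the liver safety output.

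**Working it through.** The plan states no figure on this point, so the check sets the rules side by side and follows one record through them.

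1. **Is the repeat off-schedule?** In the protocol's Table 9–1, visits from Week 4 to Week 24 are four weeks apart, each with a window of ±2 days. A repeat within 48 hours of a scheduled sample will usually be an extra, unscheduled result. It can fall inside the triggering visit's window, but the SAP does not say how a laboratory repeat would then be labelled.
2. **Does any rule bring it into a table?** None was found. SAP 8.1.3, 8.1.6, Appendices E and F, and the changes listed in SAP section 9 contain nothing that does so.
3. **Who can be affected?** If all repeat values are normal, no limit is crossed and nothing is lost. A loss needs a repeat that crosses a limit not already crossed at a scheduled visit. Such a man is discontinued and, under Protocol 9.3.7, has an end-of-treatment visit within 7 days. That visit includes blood chemistry and is a scheduled, tabulated visit. He is missed only if the value is back below the limit by then and does not cross it at any other scheduled sample.

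Worked record (all values assumed, in multiples of ULN):

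| Sample | ALT | Bilirubin | Tabulated under 8.1.7? |
|---|---|---|---|
| Week 4, scheduled | 1.2 | 0.8 | yes |
| Week 8, scheduled (trigger) | 6 | 0.9 | yes |
| 48-hour repeat, unscheduled | 11 | 2.3 | no |
| End of treatment | 2.5 | 1.1 | yes |

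Result by row:

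| Row | Scheduled only | All post-baseline |
|---|---|---|
| Maximum ALT | 6 | 11 |
| ALT >5xULN | yes | yes |
| ALT >10xULN | no | yes |
| Bilirubin >2xULN | no | yes |
| Combined criterion | no | yes |

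**Scale.** SAP section 5 plans 67 men per dose group. One omitted case changes 1/67 = 1.5% (exact 95% interval 0.04% to 8.0%) to 0/67 = 0% (exact 95% interval 0 to 5.4%, the upper limit being 1 − 0.025^(1/67) = 0.054).

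**Direction.** Adding samples to a count of men who ever exceeded a limit can raise it or leave it unchanged, but cannot lower it. Leaving samples out can therefore only under-count.

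**The case against.** The strongest reply is that very little is lost.

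- The scheduled value above 5xULN that prompted the repeat is still counted in every row up to 5xULN.
- The end-of-treatment sample may catch a persisting elevation.
- Protocol 12.1.4 makes an abnormality an adverse event if it is clinically significant, needs further testing, or leads to interruption or discontinuation.
- The repeat itself is in the listings.
- The sentence in 8.1.7 sits under a heading about listings and may have been meant only for by-visit tables. The table templates are in a separate document.

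All of this stands and limits the size of the point, but it does not remove it. Adverse event tables in SAP 8.7.1 count by system organ class and preferred term, not by multiple of ULN or by combined criterion. The list of events of special interest in Protocol 12.1.7 has no hepatic item. Listings give no count by arm. If 8.1.7 was meant more narrowly, the SAP does not say so, and a programmer following the text would leave the repeat out.

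A reader might also infer that the peak-testosterone tables in SAP 8.6.3.3 lose repeats that the protocol prescribes. The documents do not support that. The stopping rule in Protocol 9.3.7 rests on two consecutive scheduled visits, and Protocol 11.3.1 tells investigators not to monitor testosterone outside the protocol. The retests described concern screening (Protocol 9.1.1 and 9.3.3), or are merely permitted for an error or aberrant value with the medical monitor's approval (Protocol 9.3.4). Only an incidental unscheduled value is at risk there.

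**Conclusion.** The point holds for the liver threshold and potential Hy's law rows. Followed literally, SAP 8.1.7 leaves out a sample that the protocol itself provides for, and the result is a possible under-count in one direction only. For an arm of 67, one such man moves a row from 1.5% to 0%.

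That size is illustrative. The documents give no rate for ALT or AST above 5xULN, or for a limit crossed only on the repeat. The conclusion assumes that the repeat is recorded as an unscheduled result, that the trigger arose at a scheduled visit, and that the higher limit is not crossed at any scheduled sample, including end of treatment.

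Two stronger readings go too far. One is that such a man vanishes from the safety tables: he stays in the lower threshold rows and, where reported, in the adverse event tables. The other is that every man with a protocol repeat is affected: the haematocrit and creatinine repeats in Protocol 9.3.7 feed none of these threshold tables, and a liver repeat changes a count only when it crosses a new limit.

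**What to change.** Amend SAP 8.1.7 to say that by-visit summaries use scheduled visits only, while the subject-level liver threshold and potential Hy's law tables use all post-baseline results, scheduled and unscheduled. In 7.1.4.5 and 8.7.2.3, state that the requirement for both values to come from one visit is also met by a single unscheduled sampling date.

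For consistency, apply the same rule in SAP 8.6.3.3 to the overall maximum-testosterone category and to the ever-overshoot part of the summary given "at each visit and at least once during the study". Note there that the protocol prescribes no on-treatment testosterone repeat.

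The cost is a sentence or two in the SAP and minor programming on data already collected and listed. No clinical rule changes. The downside is that threshold counts may be slightly less favourable.

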8.2 Subject disposition

All subjects who provided informed consent will be included in a summary of subject

accountability. The number of subjects screened, the number of screen failures, the frequency and percentage of subjects randomised, in the Safety population, in the ITT population, in the PP population and in the PK population will be summarised by treatment regimen and overall.

Subject disposition information will be summarised by treatment regimen and overall. The number of subjects completing and withdrawing from the Randomisation Phase (up to and including Visit 8), number of subjects entering the extension study and the number of subjects completing and withdrawing from the study will be tabulated. Reasons for treatment discontinuation and discontinuation from the study will also be presented.

The follow-up time will be summarised descriptively.

Finally, the reasons for screen failure as reported on the eCRF will be tabulated.

8.3 Protocol deviations

The number of subjects excluded from ITT, Safety, PP and PK populations and reasons for exclusion will be summarised by treatment regimen and overall.

All protocol deviations identified will be summarised descriptively by treatment regimen and overall.

Summaries will be conducted on all subjects that were randomised

8.4 Demographics and baseline characteristics

No formal comparison between treatment regimens on demographics and baseline characteristics will be conducted.

8.4.1 Demographics

Demographic variables will be listed and summarised by treatment regimen and overall. This will include age, sex, race, weight, height and BMI. Separate summaries will be produced using the Safety, ITT and PP populations.

8.4.2 Baseline and disease characteristics

Duration of HH disease (years) and the number of subjects receiving previous treatment and each item on the Androgen Deficiency Symptom Checklist will be summarised descriptively by treatment regimen and overall.

Total testosterone at initial diagnosis, first and second screening visits and the average testosterone over the first and second screening visits will be tabulated using the Safety, PP and ITT population.

In addition baseline total testosterone (absolute values and number of subjects above and below 200 ng/dl), free testosterone (absolute values and number of subjects above and below 47 pg/mL), bioavailable testosterone (absolute values and number of subjects above and below 130 ng/dl), oestradiol, DHT, inhibin A, inhibin B, HBA1c, sex hormone binding globulin (SHBG), fasting lipid profile (total cholesterol, low density lipoprotein [LDL], triglycerides and HDL), Vitamin D, IIEF domain scores, IIEF erectile function domain severity and PROMIS sexFS domains will be summarised descriptively by treatment regimen and overall.

All Summaries will be produced using the Safety Population and PP Population unless stated.

8.4.3 Medical history

A summary of all medical history will be presented by Medical History Code (as per CRF), system organ class (SOC) and preferred term (PT), by treatment regimen and overall using Medical Dictionary for Regulatory Affairs® (MedDRA) Version 19.1 or higher. Separate summaries will be produced using the Safety and ITT populations.

In addition the number of subjects with an MRI of pituitary performed, the MRI finding (Normal, Abnormal NCS or Abnormal CS) and the number of subjects who have had a vasectomy will be summarised.

All Summaries will be produced using the Safety Population.

8.4.4 Prior, Concomitant and Follow-up medications

Prior, concomitant and follow-up medications will be coded using the World Health Organization (WHO) Drug Dictionary (March 2016 or later).

Prior, concomitant and follow-up medications will be summarised by Anatomical Therapeutic Chemical (ATC) classification level 4 and Preferred Name by treatment regimen and overall for the Safety population.

8.4.5 Concomitant Procedures

Concomitant procedures will be summarised by Procedure Name, treatment regimen and overall for the Safety population.

8.5 Extent of exposure

8.5.1 Treatment duration

Duration of treatment (in days) will be categorised in intervals (1-28, 29-56, 57-84, 85-112, 113-140, >140) and summarised descriptively by treatment regimen on the Safety population using descriptive statistics.

8.5.2 Treatment compliance

The overall treatment compliance (in %) will be presented by treatment regimen using the Safety population. The number of subjects with overall compliance <80% or >120% will be presented

8.6 Efficacy analyses

This section addresses the analyses to be conducted on the primary, secondary and exploratory efficacy variables.

All definitions relative to efficacy and exploratory endpoints are detailed in Section 7.1.3.

8.6.1 Analysis methods

For binary outcomes the proportion of subjects with a response will be summarised and compared between treatment regimens using Fisher's Exact Test.

For all continuous outcomes, where appropriate, a mixed model repeated measure model (MMRM) analysis will be performed. Analyses will include the fixed, categorical effects of treatment, visit, and treatment-by-visit interaction, as well as the continuous, fixed covariates of the associated baseline value and baseline-by-visit interaction. An unstructured covariance matrix will be used to model the within-subject errors. If the model with the unstructured covariance matrix fails to converge, other covariance structures, including Toeplitz, compound symmetry, and spatial power, will be considered. The denominator degrees of freedom will be calculated according to the Kenward-Roger method. Significance tests for treatment differences (individual BGS649 doses vs. Placebo and between BGS649 doses) will be based on least-squares means.

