To date, BGS649 has also been administered to 21 obese men with HH (8 subjects were assigned to placebo) and was found to be well tolerated without drug discontinuation or drug related serious adverse events (SAEs) (Study CBGS649A2204). This first-in-man study was a 2-part study over 12 weeks (11 treatments); Part 1 was an open-label dose finding study (weekly, individually titrated doses) and Part 2 used a fixed dose regimen (0.3 mg loading dose followed by 10 weekly fixed doses of 0.1 mg). Overall, BGS649 treatment (n=21) resulted in normalisation and maintenance of serum total testosterone, with no evidence of total testosterone peaks above the upper limit of normal (ULN). There were few SAEs reported (only during Part 2 and not considered related to the study drug) and the most commonly reported adverse events (AEs) included spontaneous penile erection and headache. Oestradiol levels were reduced by approximately 25-50% on average and gonadotropin levels (follicle stimulating hormone [FSH] and luteinising hormone [LH]) were increased in subjects treated with BGS649 (no effect observed for subjects on placebo). At the time of the interim analysis of Part 1, new data (Jones et al 2011) indicated that the variances of the homeostatic assessment of insulin resistance (HOMA-IR) were larger than assumed in the original sample size calculations and this (along with the discovery of dosing errors) contributed to the decision for early termination of Part 2 of the study.

A complete review of data obtained to date on BGS649 is presented in the most recent Investigator's Brochure (IB) and Food and Drug Administration (FDA) guidelines have been published on the use of testosterone replacement therapy (Testosterone Replacement Therapy, 2014).

This dose-ranging study aims to demonstrate the efficacy of BGS649 to normalise testosterone (to within normal lab-specific reference range i.e., total testosterone levels 300-1000 ng/dL [10.4-35 nmol/L]) in $\geq 75\%$ of a population of obese male subjects with HH after 24 weeks of double-blind treatment compared to placebo. Study CBGS649A2204 demonstrated that testosterone levels normalised within 2 to 4 weeks of dosing. However, any impact of testosterone levels on the symptoms and signs of hypogonadism is expected to take longer. Therefore, this study evaluates the normalisation of testosterone levels as a primary endpoint, along with key secondary/exploratory endpoints of clinical efficacy after 24 weeks.

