8.6.3.2 Change from Baseline in Total Testosterone

A descriptive summary table will be presented for Total Testosterone values and change from baseline in Total Testosterone by treatment regimen and visit using both ICON central lab and GLP lab assessed testosterone.

Change and percentage change from baseline in Total Testosterone up to Week 24 using the ICON central lab assessed values will be analysed using an MMRM model as described in Section 8.6.1. Least squares means and standard errors will be presented for each visit, p-value and 2-sided 95% confidence interval for treatment differences (BGS649 doses vs. Placebo) will be presented for each visit. Significance tests will be based on least-squares means using a two-sided $\alpha = .05$.

A figure presenting the least square mean change from baseline in total testosterone at each visit by treatment regimen will also be provided.

Change from baseline in Total Testosterone up to Week 12 using the GLP lab assessed values will be analysed using an ANCOVA model with treatment as a fixed effect and the associated baseline value as a covariate. Least squares means and standard errors will be presented for each visit, p-value and 2-sided 95% confidence interval for treatment differences will be presented for each visit. Significance tests will be based on least-squares means using a two-sided $\alpha = .05$.

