8.6.3.4 Change in LH and FSH

Descriptive summary tables will be presented for LH and FSH values and change from baseline in LH and FSH by treatment regimen and visit.

The change from baseline in LH and FSH up to Week 24 will be analysed via MMRM in the same manner as the change from baseline in total testosterone (see Section 8.6.3.1).

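### The hormone MMRM and the Week 12 ANCOVA assume the same variance in all four arms; if spread differs by arm, the pairwise and arm-level standard errors are biased (low severity, cheap to fix)

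*SAP*

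**What the plan says.** SAP 8.6.1 sets out the model for continuous outcomes: treatment, visit, treatment-by-visit, baseline and baseline-by-visit. On the covariance it says: "An unstructured covariance matrix will be used to model the within-subject errors". If that model fails to converge, "other covariance structures, including Toeplitz, compound symmetry, and spatial power, will be considered"; none of these is by arm. On the small-sample method: "The denominator degrees of freedom will be calculated according to the Kenward-Roger method". On contrasts: "Significance tests for treatment differences (individual BGS649 doses vs. Placebo and between BGS649 doses) will be based on least-squares means".

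SAP 8.6.3.2 applies the model to change and percentage change in total testosterone, and reports as follows: "Least squares means and standard errors will be presented for each visit, p-value and 2-sided 95% confidence interval for treatment differences". For the MMRM, the text then limits the listed differences to doses versus placebo. The GLP-lab values up to Week 12 "will be analysed using an ANCOVA model with treatment as a fixed effect and the associated baseline value as a covariate", without that limit. SAP 8.6.3.4 adds: "The change from baseline in LH and FSH up to Week 24 will be analysed via MMRM", in the same manner as testosterone.

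These sections provide no by-arm covariance, no sandwich variance, no transformation and no check of equal variance. SAP 8.1.4 sets two-sided 5% tests. Protocol 13.5.1 makes no multiplicity adjustment and calls all analyses exploratory.

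**The concern.** A common covariance matrix gives every arm the same residual variance at a visit. That variance is, in effect, the average over the arms. A contrast between two arms with above-average spread then gets too small a standard error, and a contrast between two arms with below-average spread gets too large a one.

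Unequal spread is likely for testosterone. Inclusion criterion 3 requires two values below 300 ng/dL. The primary objective is to move treated men into 300-1000 ng/dL, and SAP section 5 plans on a 90% normalisation rate. A placebo arm that stays near its entry level has less room to vary than an arm spread over the target range.

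For LH and FSH the support is thinner. Protocol 7.1 reports that both rose on drug and not on placebo in the earlier study, which describes level and not spread.

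At stake are the between-dose tests, the dose-versus-placebo intervals and p-values, and the standard errors of the arm-level least-squares means. Kenward-Roger works within the assumed covariance structure, so it does not repair one that wrongly equates the arms.

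**Working it through.** **Plan's own figure.** The documents contain no sizing or SD for the MMRM. The only sizing figure is 67 per dose group for the responder endpoint (75% v 90%, one-sided 2.5%, 85% power). The z formula gives (1.960·√0.1875 + 1.036·√0.09)²/0.15² = 59.8, and 66.3 with continuity correction, so 67 is reproduced. The exact test at 67 needs 58 responders: error 1.60%, power 87.1%. Only the arm size of 67 is used below.

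**Inputs.** Four equal arms of 67 (Protocol synopsis); complete data; two-sided 5%. All SDs are assumptions. With complete data, the unstructured MMRM with treatment-by-visit and baseline-by-visit terms reduces to an ANCOVA at each visit, so the check is made there.

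**Is unequal testosterone spread plausible?** A uniform spread over 0-300 ng/dL has SD 300/√12 = 87. For a normal distribution with 90% of values in 300-1000 ng/dL, assumed means of 450 to 650 imply SDs of about 117 to 213. The ratio is about 1.3 to 2.5. These are raw spreads and not baseline-adjusted residuals, and placebo values after entry are not capped at 300, so this is an illustration only.

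**Case A: doses share one SD, r times placebo's.** In units of placebo variance, pooled variance V = (1 + 3r²)/4.
- Dose-dose SE ratio (model/true) = √(V/r²)
- Dose-placebo SE ratio = √(2V/(1 + r²))
- Placebo-mean SE ratio = √V
- Real error = 2·(1 − Φ(1.96 × ratio))

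| r | V | dose-dose ratio | error | dose-placebo ratio | error | placebo mean |
|---|---|---|---|---|---|---|
| 1.25 | 1.42 | 0.954 | 6.2% | 1.053 | 3.9% | 1.19 |
| 1.5 | 1.94 | 0.928 | 6.9% | 1.092 | 3.2% | 1.39 |
| 2 | 3.25 | 0.901 | 7.7% | 1.140 | 2.5% | 1.80 |
| 3 | 7.00 | 0.882 | 8.4% | 1.183 | 2.0% | 2.65 |
| limit | – | 0.866 | 9.0% | 1.225 | 1.6% | – |

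**Case B: SD rises with dose.** Call the variances p < l < m < h. The pooled SE is too small for a pair exactly when that pair's summed variance exceeds the other two arms' sum.
- High-mid is always too narrow (h + m > p + l), so low-placebo is always too wide.
- High-low is always too narrow (h + l > p + m), so mid-placebo is always too wide.
- High-placebo is too narrow, and mid-low too wide, only if l + m < p + h. Otherwise they go the other way.

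The SE ratio for arms i and j is √(2V/(sᵢ² + sⱼ²)), where V is the mean of the four variances. For SDs of 75/110/160/230 ng/dL, V = (5,625 + 12,100 + 25,600 + 52,900)/4 = 24,056. For high-placebo this gives √(48,112/58,525) = 0.91. Results, with simulated error from 3,000 runs where available:

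| Pair | 75/110/160/230 | 75/150/200/250 | 75/150/175/200 |
|---|---|---|---|
| low-placebo | 1.65 (0.1%) | 1.52 (0.4%) | 1.33 |
| mid-placebo | 1.24 (1.3%) | 1.20 (2.1%) | 1.17 |
| high-placebo | 0.91 (8.0%) | 0.98 (5.0%) | 1.04 |
| mid-low | 1.13 (2.7%) | 1.02 (4.9%) | 0.96 |
| high-low | 0.86 (8.8%) | 0.88 (8.4%) | 0.89 |
| high-mid | 0.78 (12.3%) | 0.80 (12.2%) | 0.84 |

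In the first column the pooled SD is 155.1. The placebo mean's SE is therefore 155.1/75 = 2.07 times its true value, and the high-dose mean's is 155.1/230 = 0.67 times.

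**With arm-specific variances**, simulated error is 4.5-5.6% for every pair, over one equal-dose pattern (75/150/150/150) and the first two graded patterns.

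**The case against.** The strongest reply is that no SD is documented for any arm, so a large difference in spread is not established. That stands. A reader might take the SAP's overshoot table, which runs to above 2500 ng/dL, as evidence of wide spread. It is a reporting category and not an expectation. Protocol 7.1 reports no peaks above the upper limit of normal in the earlier study, and Protocol 9.2 considers such effects unlikely. For LH and FSH, entry requires only LH below the upper limit and sets no FSH limit, so the narrow-band argument carries over poorly. At an SD ratio of 1.25 the error rates are 6.2% and 3.9%, which is minor.

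A reader might also infer that between-dose intervals are always too narrow and placebo intervals always too wide. That needs equal SDs in the three active arms. The doses span a tenfold range (0.1 to 1.0 mg, SAP 3.2.1), so a graded SD is at least as plausible, and high-placebo and mid-low can then reverse. Four of the six directions survive any increasing pattern; two do not.

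Finally, the stakes are limited. The listed testosterone MMRM intervals are for doses versus placebo only, although SAP 8.6.1 still plans between-dose tests and the GLP-lab ANCOVA has no such limit. The primary, 90%-normalisation and overshoot endpoints are proportions and do not use this model. This is correct and sets the severity. It does not make the common-variance assumption sound.

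**Conclusion.** The point holds as a low-severity, cheap improvement. As written, the SAP assumes equal covariance across four arms for outcomes on which the drug is expected to act, and makes no provision for that being wrong. For testosterone, unequal spread is likely by inference from the entry cap and the target range; for LH and FSH it is only possible.

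If the active arms share an SD 1.5 to 3 times placebo's, nominal 5% becomes about 6.9-8.4% between doses and 3.2-2.0% against placebo. Under the assumed dose-graded patterns that were simulated, high-mid error reaches about 12%, and the direction for high-placebo and mid-low depends on the pattern. All of this assumes equal arms of 67 and complete data.

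The documents do not support saying that variances must differ sharply, that the bias has one direction for each type of contrast, or that the trial's primary conclusion is at risk.

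**What to change.** Before unblinding, amend SAP 8.6.1 and 8.6.3.2 as follows. For total testosterone (the MMRM and the GLP-lab ANCOVA), LH and FSH, estimate the residual covariance separately by treatment regimen (GROUP=treatment on the REPEATED statement; arm-specific residual variances in the ANCOVA), with Kenward-Roger degrees of freedom.

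If this does not converge, use in order:
1. a common correlation with arm-specific variances;
2. empirical (sandwich) standard errors;
3. the fallback structures already listed.

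The cost is a short SAP edit and a small programming change. Seven post-baseline visits give 7 × 8/2 = 28 covariance parameters per matrix, so up to 4 × 28 = 112 instead of 28. Convergence risk rises, which is why the fallback order should be fixed in advance, and degrees of freedom fall slightly. If the variances prove equal, little is lost.
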